8.4.5. Clinical Global Impression - Improvement Rating, as assessed by the Parent/Caregiver

CGI-I score data assessed by the parent/caregiver will be summarized and analyzed using the same methods used for CGI-I score data recorded by Principal Investigator as above.

8.4.6. Incidence of Status Epilepticus

The incidence of status epilepticus (SE) will be evaluated based on: 1.) those entered as serious adverse events, and 2.) Seizures lasting longer than 10 minutes from the seizure diary. A single seizure meeting more than one of these criteria will be counted once.

The number and percentage of subjects with SE during the baseline and T+M period recorded as an AE will be presented by treatment group. Statistical comparisons of the difference in incidence will be tested using a Fisher's Exact Test.

From the diary data, change from baseline in the number of seizures with duration > 10 minutes per 28 days for the baseline and T+M period will be reported. A nonparametric ANCOVA will be completed to compare active groups vs. placebo. As well, the number of unique days where status epilepticus was reported (normalized per 28 days) will be summarized and analyzed using the nonparametric ANCOVA.

All seizures recorded in the AE database as status epilepticus should also be included in the seizure diary. An edit check will be performed to identify the overlap between seizures identified as AE of SE and seizures entered into the diary as seizures > 10 min. The "calculated" number and percentage of subjects experiencing SE will be presented by treatment group, defined as individuals who experience either an AE of SE, medical treatment for SE, or a seizure lasting longer than 10 minutes. Each subject will be represented once regardless of incidence. Statistical comparisons of the differences in incidence between treatment and placebo groups will be based on Fisher's exact test.

A second calculation will present the number of incidences of SE, according to the above definition, by treatment group normalized to per 28 days. In this analysis, a single subject may have more than one episode of SE, but an episode of SE recorded as both an AE and as a seizure longer than 10 minutes will be counted as a single episode. Statistical comparisons of the differences between treatment and placebo groups will be based on a Fisher's Exact Test. A difference in percentages between baseline and the T+M period will be calculated and summarized within each treatment group.

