Part 1 consists of a 4-week baseline, 2-week titration, 12-week maintenance, and 2week taper or transition period. The 4-week Baseline Period consists of the establishment of initial eligibility during a screening visit to include an assessment of cardiac parameters (ECG and ECHO), followed by an observation period where subjects will be assessed for baseline seizure frequency based on recordings of daily seizure activity entered into a diary. Upon completion of the Baseline Period, subjects who qualify for the study are randomized (1:1:1) in a double-blind manner to receive 1 of 2 doses of ZX008 (0.2 mg/kg/day, 0.8 mg/kg/day; maximum dose: 30 mg/day [or 0.5] mg/kg/day, maximum 20 mg/day, for subjects taking concomitant STP]) or placebo. Randomization is stratified by weight (<37.5 kg, $\ge 37.5 \text{ kg}$) to ensure balance across treatment arms, and at least 25% of subjects will be in each weight group. All subjects are titrated to their blinded randomized dose over a 2-week Titration Period. Following titration, subjects continue treatment at their randomly assigned dose over a 12-week Maintenance Period. Total treatment time from the beginning of the Titration Period through the end of the Maintenance Period is 14 weeks. Subjects will have ECG and ECHO assessments at weeks 6 and 14 during the Maintenance Period. At the end of the Maintenance Period (or early discontinuation), all subjects undergo a blinded 2-week taper or transition period (Post-Dosing Follow-Up) depending on whether they exit the study or are enrolled in Part 2, the long-term open-label extension, respectively. Cardiac safety follow-up visits are performed after study drug discontinuation for early termination, or for those subjects who complete the study but do not enter the openlabel extension part. All subjects are required to have follow-ups at 3 and 6 months. Subjects enrolled in Germany, France and Netherlands will have an additional follow-up at 24 months. If there are any findings at a post-dose follow-up, a follow-up visit will be scheduled every 3 months until resolved or stabilized.

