6.6. GENERAL ASPECTS FOR STATISTICAL ANALYSIS

6.6.1. General Methods

All statistical analyses will be performed using SAS statistical software (Version 9.4 or later).

Part 1 summaries will be presented by treatment group (Placebo, ZX008 0.2 mg/kg/day ZX008 0.8 mg/kg/day).

Continuous data will be summarized using descriptive statistics including means, standard deviations, medians, lower and upper quartiles, minimum and maximum values. Categorical variables will be summarized with frequencies and percentages. Confidence intervals will be calculated for key parameters or estimates as warranted.

Two-sided statistical significance testing (α = 0.05) comparing each active treatment to placebo will be performed for the primary and secondary endpoints as described below, unless otherwise noted.

All relevant collected subject data will be included in listings. All subjects entered into the database will be included in data listings.

Unless otherwise specified in the subsequent sections, in the event of multiple assessments at a given planned time point, the latest collected value will be used for the summarization.

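### Fisher's exact test does not fit status epilepticus episodes per 28 days, a repeated-event rate: it is either invalid or a repeat of the subject-level analysis (minor; exploratory endpoint)

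*SAP*

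**What the plan says.** Section 8.4.6 (Incidence of Status Epilepticus) first defines a subject-level outcome: an SE adverse event, medical treatment for SE, or a seizure longer than 10 minutes. On this outcome, "Each subject will be represented once regardless of incidence", and active and placebo groups are compared with Fisher's exact test.

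It then continues: "A second calculation will present the number of incidences of SE, according to the above definition, by treatment group normalized to per 28 days". It adds: "In this analysis, a single subject may have more than one episode of SE". The test is nevertheless the same: "Statistical comparisons of the differences between treatment and placebo groups will be based on a Fisher's Exact Test". The paragraph closes by asking for a percentage difference between baseline and T+M, although the quantity is a rate.

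Earlier in the section, two similar quantities are handled differently. The number of diary seizures longer than 10 minutes per 28 days goes into a nonparametric ANCOVA, and "the number of unique days where status epilepticus was reported (normalized per 28 days) will be summarized and analyzed using the nonparametric ANCOVA".

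**The concern.** Fisher's exact test compares two proportions in a 2x2 table of independent units, each with or without the event. An episode count per 28 days is not such a table, and the SAP does not say what the four cells would be. The p-value would therefore depend on an unrecorded programming choice.

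If episodes are used as units, a few subjects with repeated prolonged seizures could produce a small p-value in either direction with no treatment effect. Follow-up may also differ between subjects. Entry to the mITT population (section 6.3) needs only one week of diary data, against 14 planned weeks.

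**Working it through.** **Inputs from the SAP.** Allocation 1:1:1 (section 4). T+M of 14 weeks, so 14 × 7 = 98 days (section 4). Group size 79 (section 4.2). Two-sided α of 0.05, which section 6.6.1 states for primary and secondary endpoints; it is taken here as the nominal level for SE.

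**Inputs assumed.** Mean SE episodes per subject over T+M: 0.2, 0.5, 1.0, 3.0. Within-subject clustering: none (Poisson), or negative binomial with shape k = 1, 0.5, 0.2, 0.1, where a smaller k means more clustering. The SAP gives neither quantity.

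**The plan's own figure.** The SAP states no error rate for this test. Its group size does reproduce. A t-test for a 30-point difference with SD 50, α 0.05 and 90% power needs 60 per group. Dividing by the Wilcoxon efficiency 3/π = 0.955 gives 62.8, so 63; 63 / 0.8 = 78.75, so 79.

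**Three ways to build the 2x2 table.**

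1. *Episodes versus remaining person-days.* 4000 simulated null trials per scenario, 79 versus 79 subjects, 98 days each. Type I error:

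| Mean episodes | Poisson | k=1 | k=0.5 | k=0.2 | k=0.1 |
|---|---|---|---|---|---|
| 0.2 | 0.034 | 0.053 | 0.063 | 0.130 | 0.208 |
| 0.5 | 0.040 | 0.094 | 0.147 | 0.271 | 0.404 |
| 1.0 | 0.045 | 0.150 | 0.247 | 0.416 | 0.528 |

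At mean 3.0 the error was 0.042 (Poisson) and 0.326 (k = 1); smaller k was not completed there. The simulation standard error is √(0.05 × 0.95 / 4000) = 0.003 near 0.05.

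A hand check shows where this comes from. With mean μ, negative binomial counts have variance μ + μ²/k, which is 1 + μ/k times the Poisson variance that the test in effect assumes. The error is then roughly 2 × [1 − Φ(1.96 / √(1 + μ/k))].
- μ = 0.5, k = 0.2: 1 + 2.5 = 3.5; 1.96 / √3.5 = 1.048; error about 0.29 (simulated 0.271).
- μ = 1.0, k = 0.1: 1 + 10 = 11; 1.96 / √11 = 0.591; error about 0.55 (simulated 0.528).

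The simulated values are slightly lower, in keeping with the conservatism of Fisher's test.

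2. *Episodes versus number of subjects.* Error was 0.054 (mean 0.2) and 0.123 (mean 0.5) even without clustering, rising to 0.537 (mean 0.5, k = 0.1). At mean 1.0 the table could be formed in only 27% to 31% of trials, and at mean 3.0 in none, because episodes exceed subjects.

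3. *Subjects with at least one episode.* Error 0.014 to 0.040: valid, but this is the first calculation again.

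**Comparator.** A rank test on each subject's episode count held 0.039 to 0.053 over the same scenarios. It was unadjusted, so it stands in for the rank ANCOVA and does not reproduce it.

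**The case against.** Four points can be made for the plan.

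*The inflation is not a fact about this trial.* A reader might infer that the planned test inflates the false-positive rate. The documents do not support that as stated. No cells are defined and no SE rate or dispersion is given. With unclustered episodes and equal follow-up the person-days version is not inflated, and at mean 0.2 with k = 1 or 0.5 it is barely so. This stands. Clustering is plausible, since section 8.4.7 makes provision for several prolonged seizures in one day, but it is not quantified.

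*A suitable rate analysis is largely in place.* The nonparametric ANCOVA on seizures longer than 10 minutes per 28 days covers the diary component of the SE definition, and the section expects SE recorded as an adverse event to appear in the diary too. This stands and narrows the point to the composite episode count.

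*A subject-level test may have been meant.* The percentage wording suggests it. Addendum section 4.6, for its SE sensitivity analysis, counts events and rates and then uses Fisher's test alongside the number of subjects with at least one event. But the addendum does not amend 8.4.6, and on this reading the test is redundant. The table titles do not settle it. The planned SE episode table (14.2.8.1.1) is headed as summary statistics only, but so is the addendum's sensitivity table (14.2.8.1.3), for which a test is described.

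*The endpoint is exploratory.* Sections 3.6 and 5.5 class it so, and none of the six steps in section 8.1 concerns SE. This stands. A reader might infer a threat to the efficacy conclusions; there is none.

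**Conclusion.** The specification is wrong in a narrow way. As written, the second SE calculation pairs a repeated-event rate with a test for independent binary units, so it is either invalid or redundant. Neither the output index nor the addendum corrects it.

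The size of any inflation rests on three things that the SAP does not supply: episodes as the unit, the mean episode rate, and the degree of clustering. The simulation gave every subject 98 days, so it says nothing about the effect of unequal follow-up. Severity: minor.

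**What to change.** In section 8.4.6:

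- Keep Fisher's exact test for the proportion of subjects with any SE.
- For SE episodes per 28 days, replace the Fisher sentence with the baseline-adjusted nonparametric ANCOVA on each subject's rate, as the section already does for prolonged seizures and for SE days. State the denominator of the rate.
- Replace the closing reference to percentages with the change in rate per 28 days between baseline and T+M.
- Align the titles of tables 14.2.8.1.1 and 14.2.8.1.2 with the analysis they will hold.

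The cost is two sentences and two table titles, using a method already specified. The addendum describes Cohort A analyses as completed, so for that cohort the change should be recorded there as made after database lock.

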6.7. VISIT WINDOWS

The following rules will be used to window data into treatment periods for by treatment period tabulations. For all by-visit tabulations, the nominal visit as recorded on the electronic Case Report Form (eCRF) will be used.

The following are the definitions for associating dates with the treatment periods of Part 1.

Baseline Period	The Baseline Treatment period will be the 28 days immediately prior to the date of the Study Day 1.
Double Blind	The Double-Blind Treatment Period start date is the date of
Treatment Period	first full daily dose (i.e. Study Day 1). The Double-Blind
Sell Call	Treatment Period end date is the last date the subject was on study treatment in Part 1.
Chy, Oblig	The Double-Blind Treatment Period consists of 16 weeks from first treatment start date, which includes 2 weeks of
S. S.	Titration period, 12 weeks of Maintenance period and 2 weeks of Taper/Transition period. The end date for efficacy
	analyses is the last day of Maintenance treatment, or Visit 12; the end date for safety analyses is the last day of

version 2.0	Syneos Health #1009529	7A
	Taper/Transition, which would be considered the date at Visit 15.	ation
	For subjects who discontinue early from the study, the double-blind treatment period end date for efficacy analyses will be the date at the early termination visit (Visit 12); the end date for safety analyses would be the date of Visit 13. If a taper is not conducted, the end date for both analyses would be Visit 12.	alithorization ereof.
Titration Period	The Titration Period begins on the first full day of treatment (Study Day 1) and extends through Visit 6 (when the subject has reached their randomization dose). The Titration Period applies to all subjects including placebo recipients. If a subject withdraws from the study prior to treatment in the maintenance period, all safety assessments and events up to and including the date of study withdrawal will be tabulated in the titration period.	ere .
Maintenance Period	The Maintenance Period covers the 12 weeks following the end of the titration period. It begins on the date of Visit 6 + 1 day and extends through the end of study/early termination visit (Visit 12).	
Titration + Maintenance Period (T+M)	The T+M period combines the Titration and Maintenance periods, beginning on the date of first treatment (Study Day 1) and extending through the end of study/end of treatment visit (Visit 12).	

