8.2. PRIMARY EFFICACY ENDPOINT AND ANALYSIS

8.2.1. Primary Efficacy Endpoint Definition

The Part 1 primary efficacy endpoint is the percent change from baseline in the frequency in seizures that result in drops per 28 days in the T+M period. The following seizure types from the DSD will be included in the frequency count of seizures resulting in drops, if for an individual subject, the seizure as listed in the eCRF has been confirmed and approved by the Epilepsy Study Consortium (ESC) as a 'drop seizure':

- atonic seizures [AS]
- tonic seizures [TS]
- tonic/atonic seizures [TA]
- generalized tonic-clonic seizures [GTC]
- secondarily generalized tonic-clonic [SGTC]

For each subject, the frequency of drop seizures will be calculated from all available data collected during the Baseline and T+M Periods. Subjects in the ZX008 0.8 mg/kg/day treatment group will be compared to those in the placebo on the frequency of drop seizures (DSF) during T+M adjusted for the frequency during Baseline using a non-parametric ANCOVA model.

The baseline period is the 28 days immediately preceding the date of Study Day 1. The T+M period is planned for 14 weeks. However, actual durations will be computed for

each subject based on the individual subject's start and stop dates for each period, except that if the baseline period is longer than 28 days, the frequency for the baseline period will be calculated with data from the 28 days immediately preceding the Study Day 1.

The frequency of drop seizures will be counted from the daily diary records provided by the Subject or Parent/Caregiver.

Responses to the DSD question about the frequency of seizure episodes will be handled differently according to the following response options.

Response	Number of seizures
No seizures	0
A single seizure	1
An episode of many discrete seizures	Based on the response to the Question 12 for frequency of episodes
A cluster of seizures back to back	This will be determined empirically dependent on the duration of the cluster event and the number of events reported in a discrete seizure event for subjects in the study.

Seizure Clusters

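### The planned within-arm difference in the percentage with status epilepticus subtracts a 28-day window from a planned 98-day window, so in expectation it shows a rise unless the true rate falls by more than about 71%

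*SAP*

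**What the plan says.** SAP section 8.4.6 (Incidence of Status Epilepticus) contains two kinds of summary.

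- **Percentages of subjects.** For SE reported as an adverse event: "The number and percentage of subjects with SE during the baseline and T+M period recorded as an AE will be presented by treatment group". For the calculated definition, which combines adverse event, medical treatment and diary seizures over 10 minutes: "Each subject will be represented once regardless of incidence". Both are ever/never measures.
- **Rates.** Prolonged seizures and SE days are each scaled to 28 days and analysed by rank ANCOVA. For episodes: "A second calculation will present the number of incidences of SE, according to the above definition, by treatment group normalized to per 28 days".

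The section then closes with: "A difference in percentages between baseline and the T+M period will be calculated and summarized within each treatment group". It does not say what the percentages are of, and it states no adjustment for period length.

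The windows are set elsewhere in the SAP. Section 6.7: "The Baseline Treatment period will be the 28 days immediately prior" to Study Day 1. Section 8.2.1: "The T+M period is planned for 14 weeks". Under section 6.7 the efficacy window of a subject who discontinues ends at the early termination visit.

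**The concern.** The share of subjects with at least one event grows with the time they are watched. T+M is planned to last 3.5 times as long as baseline. Subtracting one ever/never percentage from the other within an arm therefore mixes window length with any change in the underlying rate.

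The result could be a report table that shows SE becoming more common on treatment, placebo included, while the per-28-day outputs from the same section show it unchanged or falling. SE is drawn partly from serious adverse events, so a spurious rise could be read as harm, or a real reduction could be hidden.

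**Working it through.** **Inputs from the SAP.** Baseline 28 days (sections 6.7 and 8.2.1). T+M 14 weeks = 98 days (section 8.2.1). Ratio 98/28 = 3.5. Section 4.2 expects about 250 randomised in three equal arms, so about 83 per arm, and allows for 20% dropout before maintenance.

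**Assumption.** The SAP states no SE incidence, so there is no figure of its own to reproduce. Baseline risk p is varied from 2% to 20%.

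**Step 1: one constant risk shared by all subjects.** With true rate ratio RR (T+M to baseline), the expected T+M percentage is 1 − (1 − p)^(3.5 × RR).

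| Baseline p | T+M, RR = 1 | T+M, RR = 0.5 |
|---|---|---|
| 2% | 6.8% | 3.5% |
| 5% | 16.4% | 8.6% |
| 10% | 30.8% | 16.8% |
| 20% | 54.2% | 32.3% |

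For p = 10%: 1 − 0.9^3.5 = 0.308 and 1 − 0.9^1.75 = 0.168.

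**Step 2: break-even.** The expected difference is zero when 3.5 × RR = 1, so RR = 28/98 = 0.286. Any true reduction smaller than 1 − 0.286 = 71% gives an expected rise, whatever p is.

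**Step 3: unequal risk between subjects.** With gamma-distributed rates of shape k, the percentage over t baseline lengths is 1 − (1 + tλ/k)^(−k), where λ = k[(1 − p)^(−1/k) − 1]. For p = 10% and k = 0.1 (strong heterogeneity), λ/k = 0.9^(−10) − 1 = 1.868.

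- RR = 1 (t = 3.5): 18.3%.
- RR = 0.5 (t = 1.75): 13.5%.

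The rise shrinks from 20.8 to 8.3 points with an unchanged rate, and from 6.8 to 3.5 points with a halved rate. The direction is the same. Break-even stays at 0.286, because the curve depends on t alone and returns to p at t = 1.

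**Step 4: withdrawal.** Suppose 20% of an arm leaves at day 14 (half a baseline length), with p = 10%.

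- RR = 1: 0.8 × 30.8% + 0.2 × (1 − 0.9^0.5) = 25.7%.
- RR = 0.5: 0.8 × 16.8% + 0.2 × (1 − 0.9^0.25) = 14.0%.

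The rise is smaller but remains. An arm with this withdrawal shows 25.7% where a fully observed arm shows 30.8%, at the same underlying rate.

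**Step 5: chance variation.** Binomial simulation with 83 per arm, drawing baseline and T+M counts independently, gives these probabilities of an observed increase:

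| Baseline p | One arm, RR = 1 | One arm, RR = 0.5 | All three arms, RR = 0.5 in each |
|---|---|---|---|
| 2% | 0.92 | 0.63 | 0.25 |
| 5% | 0.99 | 0.78 | 0.47 |
| 10% | about 1.00 | 0.88 | 0.69 |
| 20% | about 1.00 | 0.96 | 0.88 |

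**Step 6: the rate scale.** Per 28 days, an unchanged rate gives a ratio of 1.0 and a halved rate gives 0.5 at any baseline incidence. The artefact disappears.

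**The case against.** **The wording.** The sentence does not say that the percentages are of subjects, and it closes the paragraph on the normalised episode count. That is true, and the ambiguity is itself a defect. It does not rescue the sentence, because a count per 28 days is not a percentage and the section defines no other percentage.

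**The rest of the section.** A reader might infer that this difference is how the plan analyses SE. It is not. Section 8.4.6 also plans three per-28-day summaries. The SE tables in the section 14 index are titled by episodes and days per 28 days, and the SAP addendum's SE sensitivity analysis derives events per 28 days. This stands and limits the damage.

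**Certainty.** A reader might also infer that every arm must show an increase. That holds in expectation only. With a halved rate and 5% baseline risk, one arm of 83 has about a 22% chance of showing none (1 − 0.78).

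**Size.** The largest figures rest on an assumed incidence and on identical risk in all subjects. Heterogeneity can cut the artefact by half or more, as step 3 shows.

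**Treatment comparisons.** The Fisher tests of active against placebo use the same planned windows in each arm and do not carry this artefact. Differential withdrawal can still affect them, as step 4 shows, but that is a separate and smaller matter.

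**Standing of the endpoint.** SE incidence is exploratory (section 5.5) and outside the testing hierarchy (section 8.1), and this output has no test attached. A rise in the placebo arm as well would alert a careful reader.

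**Conclusion.** The point holds in a limited form. On the natural reading, section 8.4.6 subtracts ever/never percentages over 28 and a planned 98 days with no exposure adjustment. In expectation the result is an increase when the rate is unchanged, and also for any true reduction smaller than about 71%.

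That threshold assumes a constant rate within each period and full follow-up in T+M. Early withdrawal lowers it somewhat: with 20% leaving at day 14, mean exposure is 0.8 × 98 + 0.2 × 14 = 81.2 days, and for small risks break-even is near 28/81.2 = 0.34, a reduction of about 66%. The size of the rise cannot be fixed from the SAP because no SE incidence is given. At an assumed 10% it is about 8 to 21 points with an unchanged rate and about 3.5 to 7 points with a halved rate.

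The severity is minor. One descriptive output on an exploratory endpoint can contradict the sound per-28-day summaries beside it. The primary and key secondary conclusions are unaffected.

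**What to change.** Delete the baseline-to-T+M difference in percentages from section 8.4.6. Report within-arm change as SE episodes or SE days per 28 diary days in each period, which the section already derives.

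If a percentage of subjects is wanted within arms, compare the 28-day baseline with successive 28-day blocks of T+M, among subjects observed for the whole block, and state which SE definition and which denominator the percentage uses. The between-arm T+M percentage can stay, with follow-up time shown by arm so that unequal withdrawal is visible.

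The cost is a change of SAP wording and one table row. No new data are needed.
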